14.2 Visual Acuity

The logarithm of the minimum angle of resolution (logMAR) visual acuity is assessed at each visit using an Early Treatment Diabetic Retinography Study (ETDRS) chart. Subjects should use their most recent correction to attain their visual acuity (VA).

The observed and change from baseline visual acuity will be summarized for each eye (study eye and fellow eye) using continuous descriptive statistics by visit for each treatment group and for all actively treated subjects. A subject listing of visual acuity will also be produced. This listing will include a variable that indicates if a subject had a visual acuity change from baseline of ≥0.2 on the logMAR scale.

14.3 Slit-Lamp Biomicroscopy

A slit-lamp biomicroscopy examination of the cornea, conjunctiva, anterior chamber, iris, lens, and eyelid will be performed at each visit. The results will be graded as normal, abnormal not clinically significant (NCS), or abnormal clinically significant (CS).

The results will be summarized using counts and percentages for each treatment group and for all actively treated subjects at each visit for each eye (study eye and fellow eye). Percentages will be based on the number of subjects in each treatment group with responses. Shift tables for the slit-lamp biomicroscopy parameters will also be provided comparing each follow-up visit to baseline. A subject listing of the slit-lamp biomicroscopy parameters will also be produced.

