5.5 WITHDRAWAL CRITERIA (IF APPLICABLE)

If at any time during the study the investigator determines that a subject's safety has been compromised, the subject may be withdrawn from the study.

Subjects may withdraw consent from the study at any time.

Sponsor and/or investigator may discontinue any subject for non-compliance or any valid medical reason (see Section 8.6.2).

If a subject discontinues participation in the study early, every attempt will be made to complete the exit procedures required at the final study visit (Visit 5).

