8.4.2 Unscheduled Visits

These visits may be performed in order to ensure subject safety. All procedures performed at an unscheduled visit will be recorded in the source documents and on the Unscheduled Visit eCRF pages. Any procedure indicated in the eCRF that is not performed should be indicated as "Not done."

Evaluations that may be conducted at an Unscheduled Visit include:

- Slit-lamp Biomicroscopy
- Visual Acuity
- IOP
- Urine Pregnancy Test
- Undilated Fundoscopy
- Assessment of AEs

- Assessment of concomitant medications and/or treatments
- Any other assessments needed in the judgment of the investigator

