4.1 General Study Design

This is a Phase 2, single-center, double-masked, randomized, placebo-controlled clinical study. Subjects will be randomized to one of the following treatment arms at Visit 2 (Day 1):

- IC265 Ophthalmic Solution 1%: 1 drop BID bilaterally (N=~20)
- Placebo Ophthalmic Solution (Vehicle): 1 drop BID bilaterally (N=~20)

Approximately 40 subjects will be randomly assigned to one of the two groups (1:1) to receive either IC265 Ophthalmic Solution 1% or placebo solution as topical ophthalmic drops administered bilaterally BID for 12 weeks. Subjects, Sponsor, Contract Research Organization (CRO), and site personnel will be masked to treatment assignment.

During the 14-day study run-in period prior to randomization, all subjects will receive Placebo Ophthalmic Solution (Vehicle) bilaterally BID.

During the screening period, two 90-minute exposures to the CAE will be conducted to ascertain eligibility to enter the study at Visit 1 (Day -14 \pm 2) and Visit 2 (Day 1). Subjects who qualify after the initial screening visit will enter the run-in phase, where they will self-administer vehicle BID for approximately 14 days. Those who qualify at Visit 2 (Day 1) will be randomized to receive study drug in a double-masked fashion for 84 days. Subjects will self-administer drops BID and will complete Daily diary symptom score assessments as instructed. The CAE exposure will occur at Visit 1 (Day -14 \pm 2), Visit 2 (Day 1), Visit 3 (Day 15 \pm 2), Visit 4 (Day 43 \pm 2), and Visit 5 (Day 85 \pm 4), with Pre-CAE, during CAE and Post-CAE assessments of ocular signs and symptoms. Study drug will be discontinued at Visit 5. Subjects will exit from the study at this visit.

Study visits will be referred to in all tables and listings as the scheduled visit name and planned study day corresponding to the visit to enable reviewers to understand the assessment timing without referring to the protocol visit schedule.

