| 14.1.5.1 | Study Drug Compliance | Intent-to-Treat Population |
| 14.1.5.2 | Overall Study Drug Exposure | Safety Population |
| 14.2.1.1 | Ora Calibra Corneal and Conjunctival Fluorescein Staining in Study Eye by Visit | Intent-to-Treat Population |
| 14.2.1.2 | Ora Calibra Ocular Discomfort & 4-Symptoms Questionnaire in Study Eye by Visit | Intent-to-Treat Population |

| Table Number | Title | Population |
|--------------|---|-------------------------------|
| 14.2.1.3 | Ora Calibra Ocular Discomfort Scale during the CAE in Study Eye by Visit | Intent-to-Treat Population |
| 14.2.1.4 | Ora Calibra Corneal and Conjunctival Lissamine Green Staining in Study Eye by Visit | Intent-to-Treat Population |
| 14.2.1.5 | Tear Film Break-Up Time (TFBUT) in Study Eye by Visit | Intent-to-Treat Population |
| 14.2.1.6 | Ora Calibra Conjunctival Redness in Study Eye by Visit | Intent-to-Treat Population |
| 14.2.1.7 | Ocular Surface Disease Index (OSDI) by Visit | Intent-to-Treat Population |
| 14.2.1.8 | Unanesthetized Schirmer's Test in Study Eye by Visit | Intent-to-Treat Population |
| 14.2.1.9 | Daily Diary Symptom Score | Intent-to-Treat Population |
| 14.3.1.1 | Overall Summary of Adverse Events | Safety Population |
| 14.3.1.2 | Ocular Treatment-Emergent Adverse Events by System Organ Class and Preferred Term | Safety Population |
| 14.3.1.3 | Non-Ocular Treatment-Emergent Adverse Events by System Organ Class and Preferred Term | Safety Population |
| 14.3.1.4 | Ocular Treatment-Related Treatment-Emergent Adverse Events by System Organ Class and Preferred Term | Safety Population |
| 14.3.1.5 | Non-Ocular Treatment-Related Treatment-Emergent Adverse Events by System Organ Class and Preferred Term | Safety Population |
| 14.3.1.6 | Serious Treatment-Emergent Adverse Events by System Organ Class and Preferred Term | Safety Population |
| 14.3.2 | Visual Acuity (logMAR) by Visit | Safety Population |
| 14.3.3.1 | Slit Lamp Biomicroscopy Results by Visit | Safety Population |
| 14.3.3.2 | Shifts in Slit Lamp Biomicroscopy from Baseline to Each Post-Baseline Visit | Safety Population |
| 14.3.4.1 | Undilated Fundus Exam Results by Visit | Safety Population |
| 14.3.4.2 | Shifts in Undilated Fundus Exam Results from Baseline to Each Post-Baseline Visit | Safety Population |

| Table Number | Title | Population |
|--------------|---|-------------------|
| 14.3.5 | Intraocular Pressure by Visit | Safety Population |

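### The slit-lamp tables give no worst post-baseline grade and no rule for unscheduled or early-termination exams, so they can miss corneal findings in a trial stopped for epithelial haziness

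*SAP*

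**What the plan says.** SAP 14.3 grades six structures, the cornea among them, as normal, abnormal not clinically significant (NCS) or abnormal clinically significant (CS). Results are counted per arm, visit and eye, and "Percentages will be based on the number of subjects in each treatment group with responses". For change over time, "Shift tables for the slit-lamp biomicroscopy parameters will also be provided comparing each follow-up visit to baseline". SAP Section 20 lists Table 14.3.3.1 (results by visit) and Table 14.3.3.2, titled "Shifts in Slit Lamp Biomicroscopy from Baseline to Each Post-Baseline Visit". Neither the section nor the table list has a row for the worst or any post-baseline grade. SAP 8.2.2 rules out imputation for safety endpoints.

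On visit labels, SAP 4.1 says "Study visits will be referred to in all tables and listings as the scheduled visit name and planned study day corresponding to the visit". The SAP gives no label or rule for an unscheduled exam and does not say under which visit an early-termination exam is counted.

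Protocol 8.4.2 provides for unscheduled visits: "These visits may be performed in order to ensure subject safety". Slit-lamp biomicroscopy is the first evaluation it lists, and "All procedures performed at an unscheduled visit will be recorded in the source documents and on the Unscheduled Visit eCRF pages". For early discontinuations, Protocol 5.5 commits to attempting the Visit 5 exit procedures. The visit schedules in both documents put Visit 5 and early termination in one column, with slit lamp marked before and after the CAE.

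**The concern.** SAP Section 1 says the trial was terminated because of emergent adverse events of epithelial haziness. Slit lamp is the planned safety exam that grades every cornea, whether or not anyone decides to report an adverse event. The natural safety question is how many subjects in each arm ever had a worsened cornea, and the planned tables do not answer it directly.

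After Day 1 the scheduled exams fall on Days 15, 43 and 85; the contacts on Days 8, 29 and 64 are telephone calls. A subject with eye complaints between visits would be examined, if at all, at an unscheduled visit. Suppose the cornea is normal at Visit 3, abnormal CS at an unscheduled exam on Day 25, and the subject then leaves. The Visit 3 row shows normal, and the subject is in neither the numerator nor the denominator at Visit 4. If there is no exit exam, or the finding has cleared by then, the shift may appear in neither table. If one arm loses more subjects this way, its by-visit percentages are the ones pulled down.

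The missing rule for exit exams reaches beyond individual withdrawals. Protocol 8.6.2 lists sponsor termination as a reason for discontinuation, so anyone still on study at termination would have an early exit exam, if it was done.

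**Working it through.** The plan gives no figure to reproduce: it states no expected rate of corneal findings, and SAP Section 5 says the sample size was not based on statistical considerations. The check is a reading of the layout followed by an illustration.

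**Where each kind of exam goes**

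| Slit-lamp exam | Tables 14.3.3.1 and 14.3.3.2 | Basis |
|---|---|---|
| Scheduled Visit 3, 4 or 5, attended | Yes, in that visit's row | SAP 14.3 |
| Unscheduled | Not stated | No rule in SAP 14.3 or 4.1 |
| Early termination | Not stated; plausibly Visit 5/Early Termination | Shared schedule column; no mapping rule |
| Pre-CAE or post-CAE exam at a visit | Not stated which one feeds the shift | Both are done at every visit |

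**Inputs.** n = 20 per arm (SAP Section 5). Assumed: h subjects in the arm develop an abnormal CS cornea; w of these are found only at an unscheduled exam and then leave; unscheduled exams are not tabulated; the other h − w are abnormal at the visit shown; there is no other dropout.

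**Formulas**
- A, exit exam not tabulated: (h − w)/(n − w)
- B, exit exam tabulated under Visit 5/Early Termination, finding cleared: (h − w)/n
- C, exit exam tabulated there, finding still present: h/n
- Worst post-baseline: h/n

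| h | w | A | B | C | Worst post-baseline |
|---|---|---|---|---|---|
| 2 | 1 | 1/19 = 5.3% | 1/20 = 5.0% | 2/20 = 10.0% | 10.0% |
| 4 | 0 | 4/20 = 20.0% | 4/20 = 20.0% | 4/20 = 20.0% | 20.0% |
| 4 | 2 | 2/18 = 11.1% | 2/20 = 10.0% | 4/20 = 20.0% | 20.0% |
| 4 | 4 | 0/16 = 0.0% | 0/20 = 0.0% | 4/20 = 20.0% | 20.0% |
| 6 | 4 | 2/16 = 12.5% | 2/20 = 10.0% | 6/20 = 30.0% | 30.0% |
| 8 | 4 | 4/16 = 25.0% | 4/20 = 20.0% | 8/20 = 40.0% | 40.0% |

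The gap runs from nothing (w = 0, or column C) to the whole signal (w = h in columns A and B).

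**Which baseline.** SAP 8.3 takes the last non-missing measure before randomized treatment. In Protocol 8.3.3 the post-CAE slit lamp at Visit 2 comes before randomization and the first dose, so baseline defaults to the post-CAE exam. An unscheduled exam follows no CAE exposure. A worst grade pooled over all exams against that baseline would mix resting with challenge-provoked findings.

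**The case against.** The strongest reply is that the haze is already counted elsewhere. The SAP itself calls it an adverse event. Protocol 9.1 requires clinically relevant deterioration to be recorded as an AE. SAP 14.1 counts each Safety Population subject with an ocular TEAE by preferred term whenever it occurred, and also summarizes maximum severity and TEAEs leading to treatment discontinuation. Listing 16.2.9.2 covers slit-lamp results for all randomized subjects and is readable at about 40 subjects. This stands: the events are not lost from reporting. It does not make the slit-lamp summary complete. AE entry depends on a judgement of clinical relevance, Protocol 9.1 excludes exacerbations related to dry-eye signs and symptoms, and a listing gives no count by arm.

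A reader might infer that the tables are confined to scheduled visits. The documents do not say so. SAP 14.3 and the table title refer to follow-up and post-baseline visits without that limit. The sentence in SAP 4.1 concerns labelling; read as an exclusion, it would bar unscheduled exams from the listings too.

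A reader might also infer that findings which led to withdrawal necessarily disappear. They need not. A finding at an attended Visit 3 or 4 stays in that row, and one still present at exit can appear under Visit 5/Early Termination. That route depends on the exit exam being done, being mapped there, and the finding persisting.

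Finally, a worst-grade row is not free of bias: subjects with extra exams have more chances to register a bad grade. That is fair and belongs in a footnote.

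**Conclusion.** The point holds as a gap in the examiner-graded corneal summary. What is established is a by-visit layout on subjects with responses, no worst post-baseline shift, and no stated rule for unscheduled or early-termination exams. It follows that a finding seen only off schedule, or cleared before exit, can be missing from Tables 14.3.3.1 and 14.3.3.2, and that by-visit percentages can understate the ever-affected proportion in an arm that loses affected subjects.

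The size is unknown. Every percentage above other than the planned 20 per arm rests on assumed counts, and the understatement is zero if no one is affected off schedule or leaves. The documents do not support saying that the safety comparison is biased by any particular amount, and SAP Section 17 plans no statistical testing. The change is still worth making: the data are already collected, and it yields an ever-affected count by arm that does not depend on AE judgement.

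**What to change.** Keep the by-visit rows. In SAP 14.3 and Table 14.3.3.2:

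1. Add, for each structure and separately for study eye and fellow eye, a shift from baseline to worst post-baseline grade (normal, abnormal NCS, abnormal CS), using all exams after the first randomized dose: scheduled, unscheduled and early termination.
2. Use as denominator the Safety Population subjects in the arm with at least one post-baseline exam.
3. Compare pre-CAE and unscheduled exams with the Visit 2 pre-CAE exam. Show post-CAE exams in a separate block against the Visit 2 post-CAE exam. State this as an exception to the default baseline in SAP 8.3.
4. State that early-termination exams are tabulated under Visit 5/Early Termination.
5. Footnote that subjects with unscheduled visits have more opportunities to register a worst grade.

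The cost is some programming in an existing table, from data already on the scheduled and Unscheduled Visit eCRF pages. The remaining drawback is the unequal number of exams per subject, which the footnote discloses but does not remove.

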14.4 Undilated Fundoscopy

An undilated fundoscopy examination of the vitreous, retina, macula, choroid and optic nerve will be performed at each visit. The results will be graded as normal, abnormal NCS, or abnormal CS.

The results will be summarized using counts and percentages for each treatment group and for all actively treated subjects at each visit for each eye (study eye and fellow eye). Percentages will be based on the number of subjects in each treatment group with responses. Shift tables for the undilated fundoscopy parameters will also be provided comparing each follow-up visit to baseline. A subject listing of the undilated fundoscopy parameters will also be produced.

14.5 Intraocular Pressure

Subjects' IOP will be assessed by non-contact tonometry in each eye at each visit. Results will be taken from a single measurement and will be recorded in millimeters of Mercury (mmHg).

The IOP values and changes from baseline for each eye (study eye and fellow eye) will be summarized using continuous descriptive statistics by visit and eye for each treatment group and for all actively treated subjects. A subject listing of IOP will also be produced. This listing will include identifiers which indicates if a subject had an IOP increase from baseline of ≥6 or ≥10 mmHg.

14.6 Drop Comfort Scale Assessment

Subjects' drop comfort will be assessed for each eye at Visits 2, 3, and 4 using the Ora Calibra® Drop Comfort Scale, where 0 indicates Very Comfortable and 10 indicates Very Uncomfortable.

The scale values for each eye (study eye and fellow eye) will be summarized using continuous descriptive statistics by visit and eye for each treatment group and all randomized subjects. A subject listing of drop comfort results will also be produced.

15. Other Data

15.1 Physical Examination

Physical examinations of general health, head, eye, ear, nose and throat (HEENT), and other body systems will be graded as normal, abnormal not clinically significant (NCS), or abnormal clinically significant (CS).

A subject listing that includes all physical examination results will be provided.

15.2 Visual Analog Scale

A VAS instrument measures a characteristic that spans a continuum, cannot be precisely or optimally measured by, or would lack sensitivity in distinguishing subtle changes on an ordinal scale. VAS will be administered to assess the subject's experience of ocular discomfort (unrelated to study drug instillation), where higher score indicates greater discomfort.

A subject listing that includes all VAS results will be provided.

16. Interim Analyses

There will be no interim analyses in this study. To note, the study was terminated early on 16NOV2023.

17. Changes from Protocol-Stated Analyses

Changes from the protocol-stated analyses, due to early termination of the study on 16NOV2023, include the following:

- Per Protocol population will not be determined.
- No imputation will be used for efficacy or safety endpoints. Specifically, the ITT population will not be analyzed using the Last Observation Carried Forward (LOCF) imputation method and multiple imputation.
- Sensitivity analyses will not be conducted as the PP population has been removed and no imputation will be used.
- Statistical testing will not be conducted. Descriptive statistics will be utilized for the efficacy and safety endpoints.

18. References

- ICH Harmonised Tripartite Guideline: Statistical Principles for Clinical Trials E9. International Council for Harmonisation of Technical Requirements for Pharmaceuticals for Human Use. 05 February 1998.
- 2. *ICH Harmonised Tripartite Guideline: Structure and Content of Clinical Study Reports E3*. International Council for Harmonisation of Technical Requirements for Pharmaceuticals for Human Use. 30 November 1995.

19. Revision History

Documentation of revision to the SAP will commence after approval of the final version 1.0.

20. Tables

Tables that will be included in the topline delivery are shown in boldface font.

| Table Number | Title | Population |
|--------------|---|-------------------------------|
| 14.1.1 | Subject Disposition | All Screened Subjects |
| 14.1.2 | Protocol Deviations | Intent-to-Treat Population |
| 14.1.2.1 | Demographics | Intent-to-Treat Population |
| 14.1.2.2 | Demographics | Safety Population |
| 14.1.3.1 | Ocular Medical History | Safety Population |
| 14.1.3.2 | Non-Ocular Medical History | Safety Population |
| 14.1.4.1 | Ocular Concomitant Medications | Intent-to-Treat Population |
| 14.1.4.2 | Non-Ocular Concomitant Medications | Intent-to-Treat Population |
| 14.1.5.1 | Study Drug Compliance | Intent-to-Treat Population |
| 14.1.5.2 | Overall Study Drug Exposure | Safety Population |
| 14.2.1.1 | Ora Calibra Corneal and Conjunctival Fluorescein Staining in Study Eye by Visit | Intent-to-Treat Population |
| 14.2.1.2 | Ora Calibra Ocular Discomfort & 4-Symptoms Questionnaire in Study Eye by Visit | Intent-to-Treat Population |

| Table Number | Title | Population |
|--------------|---|-------------------------------|
| 14.2.1.3 | Ora Calibra Ocular Discomfort Scale during the CAE in Study Eye by Visit | Intent-to-Treat Population |
| 14.2.1.4 | Ora Calibra Corneal and Conjunctival Lissamine Green Staining in Study Eye by Visit | Intent-to-Treat Population |
| 14.2.1.5 | Tear Film Break-Up Time (TFBUT) in Study Eye by Visit | Intent-to-Treat Population |
| 14.2.1.6 | Ora Calibra Conjunctival Redness in Study Eye by Visit | Intent-to-Treat Population |
| 14.2.1.7 | Ocular Surface Disease Index (OSDI) by Visit | Intent-to-Treat Population |
| 14.2.1.8 | Unanesthetized Schirmer's Test in Study Eye by Visit | Intent-to-Treat Population |
| 14.2.1.9 | Daily Diary Symptom Score | Intent-to-Treat Population |
| 14.3.1.1 | Overall Summary of Adverse Events | Safety Population |
| 14.3.1.2 | Ocular Treatment-Emergent Adverse Events by System Organ Class and Preferred Term | Safety Population |
| 14.3.1.3 | Non-Ocular Treatment-Emergent Adverse Events by System Organ Class and Preferred Term | Safety Population |
| 14.3.1.4 | Ocular Treatment-Related Treatment-Emergent Adverse Events by System Organ Class and Preferred Term | Safety Population |
| 14.3.1.5 | Non-Ocular Treatment-Related Treatment-Emergent Adverse Events by System Organ Class and Preferred Term | Safety Population |
| 14.3.1.6 | Serious Treatment-Emergent Adverse Events by System Organ Class and Preferred Term | Safety Population |
| 14.3.2 | Visual Acuity (logMAR) by Visit | Safety Population |
| 14.3.3.1 | Slit Lamp Biomicroscopy Results by Visit | Safety Population |
| 14.3.3.2 | Shifts in Slit Lamp Biomicroscopy from Baseline to Each Post-Baseline Visit | Safety Population |
| 14.3.4.1 | Undilated Fundus Exam Results by Visit | Safety Population |
| 14.3.4.2 | Shifts in Undilated Fundus Exam Results from Baseline to Each Post-Baseline Visit | Safety Population |

| Table Number | Title | Population |
|--------------|---|-------------------|
| 14.3.5 | Intraocular Pressure by Visit | Safety Population |
| 14.3.6 | Ora Calibra Drop Comfort Scale by Visit | Safety Population |

21. Listings

Listings that will be included in the topline delivery are shown in boldface font.

| Listing Number | Title | Population |
|----------------|--|----------------------------|
| 16.1.7 | Randomization Schedule | All Randomized Subjects |
| 16.2.1.1 | Subject Dispositions | All Randomized Subjects |
| 16.2.1.2 | Inclusion/Exclusion Criteria | All Screened Subjects |
| 16.2.2 | Protocol Deviations | All Randomized Subjects |
| 16.2.4.1 | Demographics | All Randomized Subjects |
| 16.2.4.2 | Medical History | All Randomized Subjects |
| 16.2.4.3 | Prior and Concomitant Medications | All Randomized Subjects |
| 16.2.4.4 | Concomitant Procedures | All Randomized Subjects |
| 16.2.5.1 | Study Drug Assignment and Accountability | All Randomized Subjects |
| 16.2.5.2 | Study Drug Exposure and Dosing Compliance | All Randomized Subjects |
| 16.2.5.3 | Study Drug Instillation | All Randomized Subjects |
| 16.2.6.1 | Ora Calibra Corneal and Conjunctival Fluorescein Staining | All Randomized Subjects |
| 16.2.6.2 | Ora Calibra Ocular Discomfort & 4-Symptom Questionnaire | All Randomized Subjects |
| 16.2.6.3 | Ora Calibra Ocular Discomfort Scale during the CAE | All Randomized Subjects |

| Listing Number | Title | Population |
|----------------|---|--|
| 16.2.6.4 | Ora Calibra Corneal and Conjunctival Lissamine Green Staining | All Randomized Subjects |
| 16.2.6.5 | Tear Film Break-Up Time (TFBUT) | All Randomized Subjects |
| 16.2.6.6 | Ora Calibra Conjunctival Redness | All Randomized Subjects |
| 16.2.6.7 | Ocular Surface Disease Index (OSDI) | All Randomized Subjects |
| 16.2.6.8 | Unanesthetized Schirmer's Test | All Randomized Subjects |
| 16.2.6.9 | Daily Diary Symptom Score | All Randomized Subjects |
| 16.2.7.1 | All Adverse Events | All Randomized Subjects |
| 16.2.7.2 | Serious Adverse Events | All Randomized Subjects |
| 16.2.7.3 | Adverse Events Leading to Study Treatment Discontinuation | All Randomized Subjects |
| 16.2.8.1 | Urine Pregnancy Test Results | All Randomized Female Subjects of Childbearing Potential |
| 16.2.9.1 | Visual Acuity (VA) | All Randomized Subjects |
| 16.2.9.2 | Slit-Lamp Biomicroscopy | All Randomized Subjects |
| 16.2.9.3 | Undilated Fundoscopy | All Randomized Subjects |
| 16.2.9.4 | Intraocular Pressure (IOP) | All Randomized Subjects |
| 16.2.9.5 | Ora Calibra Drop Comfort Scale | All Randomized Subjects |
| 16.2.9.6 | Ora Calibra Ocular Discomfort Scale outside the CAE | All Randomized Subjects |
| 16.2.9.7 | Physical Examination | All Randomized Subjects |

| Listing Number | Title | Population |
|----------------|---------------------------|----------------------------|
| 16.2.9.8 | Visual Analog Scale (VAS) | All Randomized Subjects |

22. Figures

| Figure Number | Title | Population |
|---------------|-------|------------|
| | | |

23. Appendices

